6.6. Hepatotoxicity Stopping and Rechallenge Rules

Subjects with abnormal hepatic laboratory values (*e.g.*, ALP, AST, ALT, total bilirubin, or INR) or signs/symptoms of hepatitis may meet the criteria for withholding of investigational product. Withholding is either permanent or conditional depending upon the clinical circumstances discussed below (as specified in the Guidance for Industry Drug-Induced Liver Injury: Premarketing Clinical Evaluation, July 2009).

Criteria for Permanent Withholding of KRT-232 (AMG 232) Due to Potential Hepatotoxicity

KRT-232 (AMG 232) should be permanently withheld and the subject should be followed according to the recommendations in APPENDIX C if ALL of the criteria below are met:

- Increased AST or ALT from the relevant baseline value as specified below:
 - Baseline AST/ALT level is $< 1 \times$ ULN and AST/ALT is elevated $> 3 \times$ ULN
 AND
 - Total bilirubin level is $> 2 \times$ ULN or INR is > 1.5
 AND
 - No other cause for the combination of the above laboratory abnormalities is immediately apparent; important alternative causes for elevated AST/ALT and/or elevated total bilirubin values include, but are not limited to:
 - Hepatobiliary tract disease
 - Viral hepatitis (*e.g.*, hepatitis A/B/C/D/E, Epstein-Barr virus (EBV),

cytomegalovirus (CMV), herpes simplex virus (HSV), varicella, toxoplasmosis, and parvovirus)

- Right sided heart failure, hypotension or any cause of hypoxia to the liver causing ischemia
- Exposure to hepatotoxic agents/drugs including herbal and dietary supplements, plants, and mushrooms,
- Heritable disorders causing impaired glucuronidation (*e.g.*, Gilbert's syndrome, Crigler-Najjar syndrome) and drugs that inhibit bilirubin glucuronidation (*e.g.*, indinavir and atazanavir)
- Alpha-one antitrypsin deficiency
- Alcoholic hepatitis
- Autoimmune hepatitis
- Wilson's disease and hemochromatosis
- Nonalcoholic steatohepatitis (NASH) or other "fatty liver disease"
- Non-hepatic causes (*e.g.*, rhabdomyolysis and hemolysis).

Criteria for Conditional Withholding of KRT-232 (AMG 232) due to Potential Hepatotoxicity

For subjects who do not meet the criteria for permanent withholding of KRT-232 (AMG 232) outlined above and with no underlying liver disease and eligibility criteria requiring normal transaminases and total bilirubin level at baseline or subjects with underlying liver disease and baseline abnormal transaminases, the following rules are recommended for conditional withholding of KRT-232 (AMG 232)

- Elevation of either AST/ALT according to the following schedule:
 - AST/ALT baseline value is any AND AST/ALT is elevated to any of the following values:
 - $>8 \times \text{ULN}$ at any time
 - $>5 \times \text{ULN}$ but $<8 \times \text{ULN}$ for ≥ 2 weeks
 - $>5 \times \text{ULN}$ but $<8 \times \text{ULN}$ and unable to adhere to enhanced monitoring schedule $> 3 \times \text{ULN}$ with clinical signs or symptoms that are consistent with hepatitis (such as right upper quadrant pain/tenderness, fever, nausea, vomiting, jaundice, rash, or eosinophilia ($> 5\%$)).

OR
 - Total bilirubin is $> 3 \times \text{ULN}$ at any time

OR
 - Alkaline phosphatase is $> 8 \times \text{ULN}$ at any time

KRT-232 (AMG 232) should be withheld pending investigation into alternative causes of drug-induced liver injury. If KRT-232 (AMG 232) is withheld, the subject should be followed according to recommendations for possible drug-induced liver injury in APPENDIX C. Rechallenge may be considered if an alternative cause for impaired liver tests (*i.e.*, ALT, AST, alkaline phosphatase) and/or elevated total bilirubin level is discovered and the laboratory abnormalities resolve to normal or baseline.

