+ 4	180 mg/day PO x 7 days out of 28 day cycle
+ 5	240 mg/day PO x 7 days out of 28 day cycle

If dose-de-escalation is needed for Dose level 1, Dose level -1 is defined as 30 mg/day x 7 days out of 28 day cycle.

There should be no dose modifications of KRT-232 (AMG 232) and KRd during the DLT-evaluable period (Cycle 1). Subjects requiring dose-reductions during the DLT-evaluable period will be considered a DLT.

Part B (Dose-expansion scheme)

After determination of the KRT-232 (AMG 232) MTD or proven tolerability of the highest planned dose, and a goal of 10 additional subjects will be treated in the Part 2 dose expansion in combination with KRd. The primary objective of this dose-expansion phase is to confirm the safety and tolerability of KRT-232 (AMG 232) + KRd at the MTD and tentative RP2D in a goal

of 10 subjects with relapsed and/or refractory multiple myeloma. The tentative RP2D will be determined based on the review of safety data at the MTD.

During the dose-expansion phase, subjects removed from study after Cycle 1 based on the *TP53* mutation and/or deletion status will be replaced to ensure that a goal of 10 subjects with *TP53* wild-type status are enrolled in the dose-expansion cohort.

The subject will be requested to maintain a medication diary of each dose of medication. The medication diary will be returned to clinic staff at the end of each course.

KRT-232 (AMG 232)

The following medications and/or therapies should not be administered within the timeframes specified prior to enrollment and during the study (unless otherwise specified below):

- Antitumor therapy (chemotherapy, antibody therapy, molecular targeted therapy, retinoid therapy, hormonal therapy, or investigational agent) within 21 days of study day 1; concurrent use of hormone deprivation therapy for hormone-refractory prostate cancer or breast cancer and continuation of previous hormone therapy in breast cancer subjects are permitted.
- Treatment with immune modulators including, but not limited to, corticosteroids, cyclosporine and tacrolimus within 3 weeks prior to enrollment, except for a corticosteroid dose equivalent to dexamethasone of ≤ 4 mg/day
- Therapeutic or palliative radiation therapy within 4 weeks of KRT-232 (AMG 232) day 1.

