5.6. Definition of Dose-Limiting Toxicity

A DLT is defined as any treatment emergent adverse event (TEAE) during the first treatment cycle that does not have a clear alternative cause (e.g., disease under study, concomitant therapy) based on the following criteria using NCI-CTCAE v5.0:

- Hematological toxicity
 - Grade 3 or 4 neutropenia with fever $\geq 38^0$ C lasting > 48 hours
 - Grade 4 neutropenia lasting > 7 days
 - Grade 3 or 4 thrombocytopenia associated with $>$ grade 1 bleeding. Grade 4 thrombocytopenia that persists for > 14 days, despite holding treatment
 - Grade 4 anemia, unexplained by underlying disease
 - Any other grade 4 hematologic toxicity that does not resolve to subject's pre-treatment baseline level within 72 hours
- Non-hematological toxicity
 - Grade ≥ 3 nausea, vomiting or diarrhea lasting longer than 72 hours despite optimal medical support
 - Grade ≥ 3 non-hematological toxicity (excluding increased serum creatinine, or electrolyte abnormalities that are not clinically significant and require no treatment)
 - Any grade 3 electrolyte abnormalities that do not resolve to grade ≤ 2 within 72 hours
 - Grade 3 fatigue persisting > 7 days
 - Grade ≥ 3 acute kidney injury (creatinine $> 3 \times$ baseline or > 4.0 mg/dL) lasting > 72 hours
 - Any other grade 3 or 4 non-hematologic toxicities not predefined above will be considered a DLT.
 - A delay of ≥ 14 days in commencing Cycle 2 Day 1 due to lack of adequate

recovery of KRT-232 (AMG 232) +KRD-related toxicities will be considered a DLT.

Subjects who receive < 75% of the planned study drug doses during the first cycle of (i.e. $\leq 5/7$ daily doses of KRT-232 (AMG 232) will be considered non-evaluable for purposes of determining the MTD (unless due to a DLT) and will be replaced. Subjects who experience a DLT during the DLT-evaluable period will be considered evaluable for the purposes of determining the MTD as per Section 13.1.4

Management and dose modifications associated with the above adverse events are outlined in Section 6.

Dose escalation will proceed within each cohort according to the following scheme. Dose-limiting toxicity (DLT) is defined above.

Number of Subjects with DLT at a Given Dose Level	Escalation Decision Rule
0 out of 3	Enter 3 subjects at the next dose level.

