6. DOSING DELAYS/DOSE MODIFICATIONS

This section provides guidelines for dose modification guidelines and holding parameters for KRT-232 (AMG 232), carfilzomib, lenalidomide, and dexamethasone to manage possible toxicity. There should be no dose modifications of KRT-232 (AMG 232) and KRD during the DLT-evaluable period (Cycle 1). Subjects requiring dose-reductions during the DLT-evaluable period (Cycle 1) will be considered a DLT.

Guidelines on dose-reductions for carfilzomib were based on the Carfilzomib Prescribing Information 2016 (Amgen Inc, 2016).

Guidelines on dose-reduction for lenalidomide were based on the Lenalidomide Prescribing Information 2015 (Celgene Inc, 2015).

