6.2. Dose Reductions

KRT-232 (AMG 232)

Dose Level	KRT-232 (AMG 232) Dose
- 1	30 mg/day PO x 7 days out of 28 day cycle
+ 1	60 mg/day PO x 7 days out of 28 day cycle
+ 2	90 mg/day PO x 7 days out of 28 day cycle
+ 3	120 mg/day PO x 7 days out of 28 day cycle
+ 4	180 mg/day PO x 7 days out of 28 day cycle
+5	240 mg/day PO x 7 days out of 28 day cycle

Carfilzomib

Dose Level	Carfilzomib Dose
- 2	15 mg/m ²
- 1	20 mg/m ²
+1	27 mg/m ²

Lenalidomide

Dose Level	Lenalidomide Dose
- 3	5 mg
- 2	10 mg
- 1	15 mg
+1	25 mg

Dexamethasone

Dose Level	Dexamethasone Dose
- 2	12 mg
- 1	20 mg
+ 1	40 mg

6.3. Non-Hematologic Toxicity Dose Delay/Dose Modification Guidelines.

[REDACTED]	[REDACTED]
[REDACTED]	[REDACTED]
[REDACTED]	[REDACTED]

	Management/Next Dose for KRT-232 (AMG 232)

	Management/Next Dose for KRT-232 (AMG 232)

	Management/Next Dose for KRT-232 (AMG 232)

Management/Next Dose for KRT-232 (AMG 232)	
[REDACTED]	[REDACTED]

Acute Renal Injury	Management/Next Dose for Carfilzomib
≤ Grade 1	No change in dose.
≥ Grade 2 or Creatinine clearance < 15 mL/min, or creatinine clearance decreases to less than or equal to 50% of baseline, or need for dialysis	
Withhold dose and continue monitoring renal function (serum creatinine or creatinine clearance)
 
If attributable to carfilzomib, resume when renal function has recovered to within 25% of baseline; start at 1 dose level reduction
 
If not attributable to carfilzomib, dosing may be resumed at the discretion of the physician
 
For subjects on dialysis receiving carfilzomib, the dose is to be administered after the dialysis procedure

*Subjects requiring a delay of > 4 weeks should go off protocol therapy.
 **Subjects requiring > two dose reductions should go off protocol therapy.

Hepatic Impairment	25% dose reduction in case of baseline or treatment emergent mild or moderate hepatic impairment. 
 -Withhold carfilzomib until resolved or returned to baseline. -After resolution, consider if restarting carfilzomib appropriate; may be reinitiated at a reduced dose with frequent monitoring of liver function. -If tolerated, the reduced dose may be escalated to previous dose at the discretion of the physician. -Monitor liver enzymes regularly, regardless of baseline values, and modify dose based on toxicity.

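### The DLT lists do not name a Cycle 1 liver event that permanently stops KRT-232 under 6.6, so below Grade 3 it is a DLT only indirectly

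*Combined protocol and SAP*

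**What the plan says.** **The stopping rule.** Under 6.6, "KRT-232 (AMG 232) should be permanently withheld and the subject should be followed according to the recommendations in APPENDIX C" if three things hold together: AST/ALT above 3x ULN from a baseline below 1x ULN; total bilirubin above 2x ULN or INR above 1.5; and no evident alternative explanation. Appendix C makes the same event a serious adverse event, reportable to CTEP within 24 hours. Neither place says whether it is a DLT.

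**The DLT lists.** Section 5.6 and the synopsis work by grade for non-hematologic events, ending with the catch-all "Any other grade 3 or 4 non-hematologic toxicities not predefined above will be considered a DLT". Neither contains a combined liver criterion or refers to 6.6. Section 5.6 points to Section 6 only for managing events.

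**Two routes to a DLT that need no grade.**
- A delay of at least 14 "days in commencing Cycle 2 Day 1 due to lack of adequate" recovery (5.6 and the synopsis).
- "Subjects requiring dose-reductions during the DLT-evaluable period will be considered a DLT" (5.4; repeated in the synopsis and at the start of Section 6).

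**Carfilzomib.** The hepatic impairment row in 6.3 opens with a "25% dose reduction in case of baseline or treatment emergent mild or moderate hepatic impairment". It then also says to withhold the drug until recovery and to consider restarting at a reduced dose.

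**Evaluability.** Subjects with 5 of 7 KRT-232 doses or fewer "will be considered non-evaluable for purposes of determining the MTD (unless due to a DLT) and will be replaced". Section 13.1.4 treats a subject without DLT who took at least 75% of KRT-232 doses as DLT-evaluable.

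**The concern.** Section 6.6 judges a combination of laboratory values, while 5.6 grades each toxicity separately. A combination serious enough to end the investigational drug can therefore sit below Grade 3 on every component and appear on no DLT list. Whether it counts then depends on what happens to carfilzomib or to the Cycle 2 start date, not on the liver event itself.

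The DLT count drives the 3+3 rule, and the MTD is a Part A primary objective. One uncounted subject can turn a stop into an escalation, so any error runs toward the higher dose.

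**Working it through.** **1. The band.** The 6.6 thresholds are printed. The Grade 3 cut-offs are an assumption, because the protocol adopts CTCAE v5.0 without reprinting them.

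| Component | 6.6 threshold | Assumed start of Grade 3 | Band not caught by grade |
|---|---|---|---|
| AST/ALT | >3x ULN (baseline <1x) | >5x ULN | >3x to 5x |
| Bilirubin | >2x ULN | >3x ULN | >2x to 3x |
| INR | >1.5 | >2.5 | >1.5 to 2.5 |

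The AST/ALT band must occur together with the bilirubin or the INR band, and no component may reach Grade 3. If Grade 3 starts at or below the 6.6 thresholds, the band is empty and there is no gap.

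**2. Timing (5.2, 5.4 and the 10.1 calendar).**
- KRT-232 is taken on Days 1 to 7. Carfilzomib is due on Days 1, 2, 8, 9, 15 and 16.
- Cycle 1 chemistry after first dosing is scheduled on Day 8 and Day 15 (each ±2). The earliest scheduled draw is 8 − 2 = Day 6.
- INR is scheduled only at screening, so the INR criterion depends on unscheduled testing.
- Dose fractions: 5/7 = 71.4%, below 75%; 6/7 = 85.7%, above it.

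**3. How an event in the band is scored on the visible text.**

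| When found | What happens | Score |
|---|---|---|
| While carfilzomib is still due, 6 or 7 KRT-232 doses taken (likeliest) | Carfilzomib reduction required in Cycle 1 | DLT, by the dose-reduction sentence |
| Same | Carfilzomib only withheld, KRT-232 course complete | Evaluable, no DLT, unless Cycle 2 is delayed 14 days or more |
| After the Day 16 carfilzomib dose (narrow) | No Cycle 1 carfilzomib left to reduce | No DLT unless Cycle 2 is delayed 14 days or more |
| After 5 or fewer KRT-232 doses (narrow) | KRT-232 stopped | Replaced, unless a carfilzomib reduction or the stop itself is read as a required dose reduction |

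The third row needs unscheduled chemistry or an early Cycle 2 Day 1 draw: 29 − 4 = Day 25 at the earliest. The fourth needs the Day 8 visit moved to Day 6 before dosing, or an unscheduled test. The delay route is weak for this band, because 6.1 lets the next cycle begin once related non-hematologic toxicity is Grade 2 or lower.

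**4. The plan's own figures.** The plan prints none for this point. Its only probabilities that depend on DLT counts are in 5.7. They reproduce as binomial tails at true rates of 15/30/50%: P(≥3 of 11) = 22.1/68.7/96.7% and P(≥5 of 16) = 7.9/55.0/96.2%. This point does not change them.

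**5. Illustration of size.** All rates here are assumed. Let d be the rate of other DLTs and e the rate of events in the band, independent of each other. For a per-subject counted-DLT probability p, with q = 1 − p, the chance of escalating past a dose level is q³ + 3pq² × q³ = q³ + 3pq⁵.
- Counted: p = 1 − (1 − d)(1 − e).
- Not counted: p = d.
- Replaced: p = d / (1 − (1 − d)e).

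Example with d = 15% and e = 5%. Counted: p = 1 − 0.85 × 0.95 = 0.1925, giving 0.5265 + 0.1983 = 72.5%. Not counted: 0.6141 + 0.1997 = 81.4%. The difference is 8.9 points.

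| e (d = 15%) | Counted | Not counted | Difference |
|---|---|---|---|
| 0.5% | 80.5% | 81.4% | 0.9 |
| 1% | 79.7% | 81.4% | 1.7 |
| 2% | 77.9% | 81.4% | 3.5 |
| 5% | 72.5% | 81.4% | 8.9 |
| 10% | 63.2% | 81.4% | 18.1 |

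Differences are taken before rounding. If every such subject were replaced, the chance would be 80.9/80.0/78.5% at e = 2/5/10%. At e = 5%, the counted and uncounted figures are 82.4% and 90.6% for d = 10%, and 52.0% and 60.0% for d = 25%. Each difference assumes that no event is caught by the indirect routes, so it is the most that non-counting could add at that rate.

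**The case against.** The best reply is that the likeliest case is already covered. Section 6 opens with "Subjects requiring dose-reductions during the DLT-evaluable period (Cycle 1) will be considered a DLT", and the trigger is that a reduction is required, not that a site applied one. The 6.3 hepatic row can be read as a single instruction: hold, recover, restart lower. On that reading an event found at the Day 8 or Day 15 visit is a DLT. The reading is reasonable, but the row also says to withhold and then only to consider restarting, and the DLT sentence does not mention withholding. Two sites could follow the text and score differently.

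Other points narrow the concern:
- The band rests on assumed CTCAE cut-offs.
- The KRT-232 tables in 6.3 and its adverse event list are redacted. A hidden liver row requiring a KRT-232 reduction could help. The DLT lists themselves are not redacted.
- The event is probably uncommon. The visible human and preclinical risk summary in 2.3.2 names no liver toxicity. The table of KRd reactions at 10% or more in Section 7 lists no liver event. Exposure to other hepatotoxic drugs is a named alternative cause in 6.6.
- Investigator sign-off on escalation, at least monthly calls with CTEP (12.1), the 24-hour report and the safety review before the tentative RP2D all add scrutiny. None is a rule that the event counts.
- Keeping a precautionary liver rule apart from a graded DLT list is a legitimate design. Even so, the plan should say how such an event is scored.

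A reader might infer that a permanent liver stop never counts as a DLT, or that any such event may be scored in any of three ways. The documents support neither. Grade 3 events count, the indirect routes exist, and timing limits which outcomes a given subject can have.

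**Conclusion.** The point holds as a gap in a stated decision rule, and closing it is a cheap improvement. On the visible text, and given the assumed Grade 3 cut-offs, a Cycle 1 event that permanently ends KRT-232 can be scored as evaluable without DLT when carfilzomib is only held, the seven KRT-232 doses are complete and Cycle 2 is not delayed by 14 days. Replacement is possible but narrow.

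The size is unknown. The escalation differences show direction and rough scale under assumed rates; they are not estimates for this trial. A reader might go further and infer that the MTD will be set too high. The documents do not support that: they give no event rate, and the existing routes and oversight may catch some or all of these events.

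**What to change.** Add one bullet to the DLT list in 5.6 and to the matching list in the synopsis:

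*Any Cycle 1 event meeting the Section 6.6 criteria for permanent withholding of KRT-232 is a DLT, regardless of CTCAE grade or number of KRT-232 doses taken, unless the Appendix C work-up establishes a clear alternative cause; the subject is DLT-evaluable and not replaced.*

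The exception matches the alternative-cause exemption already in the 5.6 definition. Section 13.1.4 needs no change, since it already includes any escalation subject with a DLT, and the management text in 6.3 and 6.6 can stay. No tests or visits are added.

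The cost is slightly more cohort expansion or earlier stopping of escalation, and an occasional provisional DLT call until the work-up is complete. The bullet does not reach subjects whose baseline AST/ALT is at or above 1x ULN, although eligibility allows up to 2.5x. The sponsor should decide whether to leave them to the graded list.

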7. ADVERSE EVENTS: LIST AND REPORTING REQUIREMENTS

Adverse event (AE) monitoring and reporting is a routine part of every clinical trial. The following list of AEs (Section 6.1) and the characteristics of an observed AE (Section 6.2 and 6.3) will determine whether the event requires expedited reporting via the CTEP Adverse Event Reporting System (CTEP-AERS) **in addition** to routine reporting.

7.1. Comprehensive Adverse Events and Potential Risks List (CAEPR)

The Comprehensive Adverse Event and Potential Risks list (CAEPR) provides a single list of reported and/or potential adverse events (AE) associated with an agent using a uniform presentation of events by body system. In addition to the comprehensive list, a subset of AEs, the Specific Protocol Exceptions to Expedited Reporting (SPEER), appears in a separate column and is identified with **bold** and *italicized* text. The SPEER is a list of events that are protocol-specific exceptions to expedited reporting to NCI (except as noted below). Refer to the 'CTEP, NCI Guidelines: Adverse Event Reporting Requirements'

http://ctep.cancer.gov/protocolDevelopment/adverse_effects.htm for further clarification.

NOTE: The highest grade currently reported is noted in parentheses next to the AE in the SPEER. Report **ONLY** AEs higher than this grade expeditiously. If this CAEPR is part of a combination protocol using multiple investigational agents and has an AE listed on different SPEERs, use the lower of the grades to determine if expedited reporting is required.

CAEPRs for CTEP IND Agent

7.1.1. CAEPR for KRT-232 (AMG 232)

Comprehensive Adverse Events and Potential Risks list (CAEPR) for KRT-232 (AMG 232, NSC 789723)

The Comprehensive Adverse Events and Potential Risks list (CAEPR) provides a single list of reported and/or potential adverse events (AE) associated with an agent using a uniform presentation of events by body system. In addition to the comprehensive list, a subset, the Specific Protocol Exceptions to Expedited Reporting (SPEER), appears in a separate column and is identified with bold and italicized text. This subset of AEs (SPEER) is a list of events that are protocol specific exceptions to expedited reporting to NCI (except as noted below). Refer to the 'CTEP, NCI Guidelines: Adverse Event Reporting Requirements'

http://ctep.cancer.gov/protocolDevelopment/electronic_applications/docs/aeguidelines.pdf for further clarification.
Frequency is provided based on 379 patients. Below is the CAEPR for KRT-232 (AMG 232).

NOTE: Report AEs on the SPEER **ONLY IF** they exceed the grade noted in parentheses next to the AE in the SPEER. If this CAEPR is part of a combination protocol using multiple investigational agents and has an AE listed on different SPEERs, use the lower of the grades to determine if expedited reporting is required.

Adverse Events with Possible Relationship to KRT-232 (AMG 232) (CTCAE 5.0 Term) [n= 379]

Specific Protocol Exceptions to Expedited Reporting (SPEER)

¹This table will be updated as the toxicity profile of the agent is revised. Updates will be distributed to all Principal Investigators at the time of revision. The current version can be obtained by contacting [contact]. Your name, the name of the investigator, the protocol and the agent should be included in the e-mail.

Adverse events reported on KRT-232 (AMG 232) trials, but for which there is insufficient evidence to suggest that there was a reasonable possibility that KRT-232 (AMG 232) caused the adverse event:

Term	Percentage
GMOs	85%
Organic	78%
Natural	75%
Artificial	65%
Organic	82%
Natural	79%
Artificial	68%
Organic	87%
Natural	84%
Artificial	72%
Organic	90%
Natural	88%
Artificial	70%
Organic	89%
Natural	86%
Artificial	69%
Organic	92%
Natural	89%
Artificial	73%
Organic	91%
Natural	87%
Artificial	71%
Organic	93%
Natural	90%
Artificial	74%

Note: KRT-232 (AMG 232) in combination with other agents could cause an exacerbation of any adverse event currently known to be caused by the other agent, or the combination may result in events never previously associated with either agent.

